The SF-36 is a widely used generic quality of life instrument that assesses the subject's general health and functional status. It consists of 36 questions that are grouped into 8 domains (physical functioning, vitality, social functioning, mental health, role physical, bodily pain, role emotional, and general health). Domain scores range from 0-100, with greater scores reflecting better health status. In addition, SF-36 has 2 summary scores, the Physical Component Summary (PCS) and the Mental Component Summary (MCS). The summary scores are constructed as T scores with a mean \pm SD of 50 ± 10 where 50 is the average score in the general population. Higher scores indicate better health status.

In addition to the continuous scores, the following dichotomous endpoints will be summarized:

- Proportion with improvement from baseline in Mental Component Score of ≥ 2.5 ;
- Proportion with improvement from baseline in Mental Component Score of ≥ 5 ;
- Proportion with improvement from baseline in Physical Component Score of ≥ 2.5 ;
- Proportion with improvement from baseline in Physical Component Score of ≥ 5 ;
- Work Productivity and Activity Impairment (WPAI).

The WPAI assesses work productivity and impairment. It is a 6-item questionnaire used to assess the degree to which a specified health problem affected work productivity and regular activities over the past 7 days. The questions are as follows:

Q1 = currently employed

Q2 = hours missed due to health problems

Q3 = hours missed other reasons

Q4 = hours actually worked

Q5 = degree health affected productivity while working (0-10 scale)

Q6 = degree health affected regular activities (0-10 scale)

Subscale scores that are calculated from these questions are:

Percent work time missed due to health problem: $Q2/(Q2+Q4)$

Percent impairment while working due to health problem: $Q5/10$

Percent overall work impairment due to health problem:

$Q2/(Q2+Q4)+[(1-Q2/(Q2+Q4))*(Q5/10)]$

Percent activity impairment due to health problem: Q6/10.

Each subscale score is expressed as an impairment percentage (0-100) where higher numbers indicate greater impairment and less productivity.

If a response is missing, any subscale score that requires that response will be considered missing.

- MRI SIJ/spine as measured by Spondyloarthritis Research Consortium of Canada (SPARCC).

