5.3. Methods to Manage Missing Data

Unless otherwise specified, missing items for observations on the individual items of the derived efficacy and health outcome scales will be handled as follows. If more than 20% of the items are missing, the total scores for these scales will be considered missing. If 20% or fewer items are missing, the average of the available items will be multiplied by the total number of items to get a derived total score. Similarly, if more than 20% of the items from a subscale are missing the subscale will not be used in the analysis. If 20% or fewer items are missing then the average of the available items for that subscale will be multiplied by the total number of items in the subscale to get the derived subscale score.

Where an observed case analysis is being employed, the data will be analyzed without imputation for missing visit data. Where the last observation carried forward (LOCF) approach is being employed, efficacy assessments will be handled in the following manner. If the scheduled assessment is available it will be used. If the scheduled assessment is missing, the immediately preceding assessment, scheduled or unscheduled, will be used (eg, if assessments are to be done at weeks 4, 8 and 12 and data are available at weeks 4 and 12 but week 8 is missing, then the week 4 value will be carried forward to week 8). Baseline data will not be carried forward unless otherwise noted. For composite endpoints, missing components will not be carried forward to complete a composite endpoint with partial data available; only the complete composite endpoint value will be carried forward.

Missing values for safety endpoints will not be imputed.

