6.2.2. Continuous endpoints

Endpoints: ASDAS ESR and ASDAS CRP, BASDAI total and components, BASFI total and components, BAS-G total, SAGA, PGA, tender and swollen joint counts, dactylitis (total and number of affected digits) and enthesitis (MASES) scores, ESR, CRP, EQ-5D index and EQ-5D VAS, SF36 PCS and MCS, WPAI (4 derived subscales totals), SPARCC (SIJ and 6DVU).

- Analysis time points: All Period 1, 2 and 3 scheduled visits.
- Analysis population (method of imputation for missing data): FAS (LOCF and observed cases), where FAS populations are defined in each period in [Section 4.1](#).
- Analysis methodology: Change from baseline will be summarized using the methods specified in [Section 5.2.2](#).
- Supporting objective and Decision rule: Secondary Objectives.

Reporting results:

- Raw data: The sample size, mean, standard deviation, 95% CIs, minimum, maximum, median and 25th and 75th percentile values will be presented.
- Change from baseline: The sample size, mean, standard deviation, 95% CIs, minimum, maximum, median and 25th and 75th percentile values will be presented. Changes from period 1 baseline will be presented for all periods. For period 2 and 3, changes from the respective period baselines will also be presented.

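### The WPAI missing-response rule has no exception for subjects who worked no hours: if Q5 is left blank, it discards an overall work impairment score that the SAP formula fixes at 100%

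*SAP*

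**What the plan says.** SAP section 3.2 (WPAI) defines the inputs. Two are counts of hours: "Q2 = hours missed due to health problems" and "Q4 = hours actually worked". The third is "Q5 = degree health affected productivity while working (0-10 scale" (the closing bracket is cut off here). Percent work time missed is Q2 divided by Q2 + Q4. Percent overall work impairment adds to that fraction the remaining fraction multiplied by Q5/10. On direction and range, the section says: "Each subscale score is expressed as an impairment percentage (0-100) where higher numbers indicate greater impairment and less productivity".

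The WPAI text ends with its own missing-data rule: "If a response is missing, any subscale score that requires that response will be considered missing". The 20% item rule in SAP section 5.3 applies only where nothing else is specified, so the WPAI rule takes precedence.

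SAP section 6.2.2 summarises all four WPAI subscales as continuous endpoints at the scheduled visits of all three periods, by observed cases and by LOCF. For LOCF, section 5.3 says: "If the scheduled assessment is missing, the immediately preceding assessment, scheduled or unscheduled, will be used". Baseline values are not carried forward, and a composite is carried only as a complete value, so a missing Q5 cannot be filled in on its own.

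**The concern.** The rule treats Q5 as needed in every case. There is one case where it is not: an employed subject who lost the whole recall week to ill health. Such a subject has no working time to rate, so a blank Q5 would be a natural response. The overall score is nevertheless fully determined by Q2 and Q4, and it is the worst score on the scale.

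Read literally, the rule sets that score to missing when Q5 is blank. Because only the maximum can be lost in this way, the error in the visit mean goes one way, towards less impairment.

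Subject-level results can also contradict each other. Percent work time missed does not use Q5, so it stays at 100%, while LOCF can place a lower overall impairment beside it. The SAP formula never allows overall impairment to be below work time missed.

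**Working it through.** **Inputs.** The formula, the missing-response rule and the LOCF rule come from SAP sections 3.2 and 5.3. The share of affected subjects, the mean of the others and the carried-forward values are assumptions, because neither document gives them. The SAP has no worked WPAI example to reproduce.

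**Step 1: the formula when no hours were worked.** Let A = Q2/(Q2 + Q4). Overall impairment = 100 × [A + (1 − A) × Q5/10].

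With Q2 = 40 and Q4 = 0, A = 1 and 1 − A = 0. The result is 100 × [1 + 0 × Q5/10] = 100% for every Q5 from 0 to 10. Q2 = 8 with Q4 = 0 also gives 100%.

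**Step 2: is this the only such case?** The spread caused by Q5 is 100 × (1 − A).

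| Hours missed / worked | Score at Q5 = 0 | Score at Q5 = 10 | Spread |
|---|---|---|---|
| 40 / 0 | 100 | 100 | 0 |
| 39 / 1 | 97.5 | 100 | 2.5 |
| 32 / 8 | 80 | 100 | 20 |
| 20 / 20 | 50 | 100 | 50 |
| 0 / 40 | 0 | 100 | 100 |

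Once any hours are worked, Q5 matters and the missing-response rule is reasonable. The exception is confined to Q2 > 0 with Q4 = 0.

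**Step 3: one subject under LOCF.** Previous post-baseline visit: Q2 = 0, Q4 = 40, Q5 = 2, so A = 0 and the score is 100 × 2/10 = 20%. Current visit: Q2 = 40, Q4 = 0, Q5 blank. The rule gives missing and LOCF gives 20%, where the formula gives 100%. Work time missed at the same visit is 40/40 = 100%. Earlier values of 20, 40, 60 or 80 understate this subject by 80, 60, 40 or 20 points. If 5% of subjects were affected, the LOCF mean would fall by 4.0, 3.0, 2.0 or 1.0 points. An earlier value of 100% would cause no error.

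**Step 4: observed-case mean.** Let k be the share of employed subjects with Q2 > 0, Q4 = 0 and Q5 blank, and m the mean of the others. The full mean is 100k + (1 − k)m and the reported mean is m, so the shortfall is k × (100 − m).

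| m (assumed) | k = 1% | k = 2% | k = 5% | k = 10% |
|---|---|---|---|---|
| 20 | 0.8 | 1.6 | 4.0 | 8.0 |
| 30 | 0.7 | 1.4 | 3.5 | 7.0 |
| 50 | 0.5 | 1.0 | 2.5 | 5.0 |

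**Step 5: baselines.** The protocol's Schedule of Activities first collects WPAI on Day 1, not at screening. The screening fallback in SAP section 3.4 therefore cannot replace a missing Day 1 score, and the subject has no change from Period 1 baseline on this subscale. At R0 the position differs. Section 3.4 takes the last Period 2 value before re-treatment as the Period 3 baseline, so a missing R0 score falls back to an earlier Period 2 value where one exists. Section 5.2.2 also reports Period 3 changes from the Period 1 baseline, which do not depend on R0.

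**The case against.** The strongest objection is that the decisive condition is not in the documents. Neither reproduces the questionnaire, its skip instructions or a data-entry convention for zero hours worked. If Q5 is answered, the formula returns 100% and nothing is lost. This stands: a reader might infer that the rule drops every subject who missed the whole week, and the documents do not support that. They support only the conditional statement.

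It can also be argued that Q5 is not a required response when its weight is zero, so the rule already permits 100%. That reading is possible. But the SAP does not give it, and the formula names Q5 without qualification, so a programmer following the text would set the score to missing. The ambiguity is itself a reason to settle the point.

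A third objection is that the subject is not lost from WPAI altogether. Work time missed (100%) and activity impairment (Q6/10) are still scored. This is correct, and it confines the problem to one subscale.

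Finally, a reader might infer that improvement on etanercept, loss after withdrawal and gain on retreatment are all understated. That would need full absence to cluster at Day 1 and at flare, which the documents do not show. A 100% score lost at a later Period 1 visit and replaced by a lower value would instead overstate improvement.

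**Conclusion.** The point holds as a conditional gap in a scoring rule. If Q2 > 0, Q4 = 0 and Q5 is blank, the SAP sets to missing a score that its own formula fixes at 100%. The observed-case mean at that visit is then understated by k × (100 − m). Over the assumed ranges in the working this is 0.5 to 8.0 points; those figures illustrate the formula and are not evidence of frequency. Under LOCF the substituted value can only be equal or lower, and with no earlier post-baseline value the subject drops out there too.

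The net direction of bias in change scores is not derivable. Nor should a reader infer that a missing R0 score removes all change scores: the Period 3 baseline falls back to an earlier Period 2 value, and change from Period 1 baseline remains available. Only a Day 1 loss removes change from Period 1 baseline.

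The subscale is a descriptive secondary measure. The flare estimate, time to flare and the sample size are untouched. This is a minor clarification worth making because it costs almost nothing.

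**What to change.** Add to the WPAI derivation in SAP section 3.2: *If Q1 = yes, Q2 > 0 and Q4 = 0, percent overall work impairment = 100% whether or not Q5 is answered; percent impairment while working is missing if Q5 is blank.* Keep the missing-response rule for all other cases.

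The same edit could state how Q2 = Q4 = 0 is handled, where the ratio is 0/0. That is a separate, optional point.

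The cost is one SAP sentence and one line of derivation code. No new data are needed and no other analysis changes.

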### **5.1. Allocation to Treatment**

This is an open-label study; however, subjects must also receive a treatment assignment number. Enrollment will be accomplished using interactive response technology (IRT), an automated web/telephone system. At the screening visit, the investigative site will contact the IRT (online or by telephone call). The site will enroll the subject into the IRT by indicating minimal information sufficient to distinguish one subject from another and receive the unique Subject identification (ID) number. A subject who discontinues or is withdrawn from the study before receiving a treatment assignment code and who re-enrolls at a later time must be assigned a new unique Subject ID number. A Subject ID number must never be reassigned or reused for any reason. At the baseline visit, enrollment will be accomplished by the IRT system, which will allocate a drug package to the subject.

All subjects will have the option of discontinuing the study at any time (eg, for flare or if the subject and/or treating physician feels that it is in the best interest of the subject to do so). Subjects who are screen failures or discontinue must have their statuses changed in the IRT system.

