#### **9.1. Sample Size Determination**

The focus of this open label study is estimation. The sample size for this study was determined based on both the primary and key secondary endpoints. For the primary endpoint, 70% of subjects are expected to flare following treatment withdrawal. With an enrollment of approximately 200 subjects, approximately 96 subjects are expected to enter the treatment withdrawal period. If 70% of subjects with treatment withdrawn flare, the half width of the 95% confidence interval on flare rate estimate will be approximately 10%. For the key secondary endpoint of retreatment response, it is anticipated that 60% of the subjects who flare and are retreated will recover the initial ASDAS less than 1.3 response. The half-width confidence interval on this estimate will be approximately 12%.

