Scoring of sacroiliac joints will also use the SPARCC method. Scoring will be based on 6 consecutive coronal slices from posterior to anterior.

Each joint will be divided into 4 quadrants. Each quadrant will be assigned a score of 0 = no lesion or 1 = increased signal. This part of the scoring allows for a total score ranging from 0-8 for the 2 joints of one coronal slice. For each slice, the score is increased by 1 for each joint that exhibits an intense signal in any quadrant (thereby allowing for an increase of up to 2 points in the total score for each slice). Also, for each slice, an additional score of 1 will be given for each joint that includes a lesion demonstrating continuous increased signal of a depth ≥ 1 cm from the articular surface (thereby allowing for an additional increase of up to 2 points for each slice). Therefore, the maximal score for each coronal slice is 12 and the maximum score for 6 slices is 72.

The following secondary endpoint will be estimated over 12 weeks following re-treatment of patients who flare:

- Time to ASDAS inactive disease after re-treatment.

Subjects are required to have flared to enter the retreatment period. This endpoint is the time from first dose of retreatment until the first observed event of ASDAS inactive disease. Subjects who do not achieve ASDAS inactive disease will be censored at the time of the last ASDAS evaluation in the interval.

Other endpoints:

- Subject Assessment of Disease Activity (SADA).

Change from baseline in Subject Assessment of Disease Activity - VAS at each visit. Subjects will assess the overall disease activity over the last 48 hours by placing a mark that corresponds to the magnitude of their pain on a 100 mm pain scale that ranges from 0 mm (none) to 100 mm (severe). The reported values will be converted to cm for analysis purposes.

- Physician Global Assessment (PGA).

Change from baseline in VAS Physician Global Assessment at each visit. The investigator will estimate the subject's overall disease activity over the last 48 hours by placing a mark on a 100 mm scale that ranges from 0 mm (none) to 100 mm (severe). The reported values will be converted to cm for analysis purposes.

- Bath Ankylosing Spondylitis Patient Global Assessment Score (BAS-G).

The BAS-G consists of 2 questions:

How have you been over the last week?

How have you been over the last six months?

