5.1. Hypotheses and Decision Rules

This study is an open-label study with one treatment group. Inferences will be based on point estimates and confidence intervals, rather than on hypothesis tests.

Except where stated, all confidence intervals will be 2-sided 95% confidence intervals.

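### Time to inactive disease on retreatment: censoring subjects who stop early can overstate recovery if those who stop are less likely to recover, and the SAP names no estimator or sensitivity analysis

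*SAP*

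**What the plan says.** SAP 3.2 lists one secondary endpoint specifically for retreated subjects, time to ASDAS inactive disease: "The following secondary endpoint will be estimated over 12 weeks following re-treatment of patients who flare". It defines it as follows: "This endpoint is the time from first dose of retreatment until the first observed event of ASDAS inactive disease". For everyone else it says: "Subjects who do not achieve ASDAS inactive disease will be censored at the time of the last ASDAS evaluation in the interval". The rule makes no distinction by reason or by whether the subject reached R12.

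The SAP does not say how this endpoint is to be estimated. SAP 5.2.4 gives Kaplan-Meier, life-table and Cox methods for flare only, and SAP section 6 has no entry for time to inactive disease. No sensitivity analysis of its censoring is planned.

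Recovery on retreatment is also summarised as a plain proportion with a 95% interval (Protocol 9.2.2). SAP 6.2.1 reports it at each Period 3 visit, by LOCF and by observed cases. The planning figures in Protocol 9.1 belong to that proportion: "it is anticipated that 60% of the subjects who flare and are retreated will recover the initial ASDAS less than 1.3 response", with a half-width of about 12%.

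Subjects can leave Period 3 early. Protocol 5.1 says: "All subjects will have the option of discontinuing the study at any time". Protocol 5.2 discontinues subjects who miss more than two consecutive doses. Protocol 6.8 withdraws subjects for related toxicity, for serious infection, or when the investigator judges that a non-permitted medication is indicated.

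**The concern.** The event here is a good outcome. A censoring-based estimator lets the subjects still followed stand in for those censored. For a subject who completes R12 without recovering, that is ordinary administrative censoring and does no harm. For a subject who stops retreatment at, say, R4 because it is not working or not tolerated, it credits that subject with the later recovery chance of those who continued. Several of the exits listed above are linked to doing badly or to being off drug, so the assumption of equal later recovery is doubtful, and the likely direction of error favours the drug.

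Whether response can be regained after a flare is a stated secondary objective. The same report could also show two 12-week recovery figures that treat the same stoppers differently: non-responders in the LOCF proportion, censored in the curve.

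**Working it through.** **The plan's own figure.** Protocol 9.1 says "approximately 96 subjects are expected to enter the treatment withdrawal period" and "70% of subjects are expected to flare following treatment withdrawal". That gives 0.70 × 96 = 67.2, about 67 retreated. At 60% recovery, with two-sided 95% intervals (SAP 5.1), the half-width is 1.96 × √(0.60 × 0.40 / 67) = 11.7%. The stated 12% reproduces. It applies to the proportion and does not depend on the censoring rule, so it serves below only as a yardstick.

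**Assumptions.** The documents give neither a Period 3 dropout rate nor the timing of recovery. I take 67 retreated and 40 observed to recover (40/67 = 59.7%), with 20, 12 and 8 first recoveries at R4, R8 and R12. Let k4 and k8 be the numbers who stop without inactive disease after R4 and after R8. All of them are assumed to be non-achievers who would not have recovered.

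**Formulas under the stated rule with Kaplan-Meier.**

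Recovery by R8 = 1 − (1 − 20/67) × (1 − 12/(47 − k4))

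Recovery by R12 = 1 − (1 − 20/67) × (1 − 12/(47 − k4)) × (1 − 8/(47 − k4 − 12 − k8))

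| Stoppers (k4, k8) | By R8 | By R12 | Excess over 59.7% (points) |
|---|---|---|---|
| 0 (0, 0) | 47.8% | 59.7% | 0 |
| 4 (2, 2) | 48.6% | 61.8% | 2.1 |
| 7 (4, 3) | 49.4% | 63.9% | 4.2 |
| 10 (5, 5) | 49.9% | 65.9% | 6.2 |
| 13 (7, 6) | 50.9% | 68.8% | 9.1 |

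For the last row: (47/67) × (28/40) × (14/22) = 0.312, and 1 − 0.312 = 0.688.

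**Median.** With stoppers kept as non-achievers, recovery by R8 is 32/67 = 47.8%, so the median falls at R12. Under the stated rule the curve passes 50% at R8 only with 13 stoppers. In the other rows the median stays at R12.

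**Sensitivity to timing.** I repeated the calculation with front-loaded (20/12/8), even (13/13/14) and late (8/12/20) recoveries, and with stopping all after R4, split, or all after R8:

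| Stoppers | Share of 67 | Kaplan-Meier recovery by R12 |
|---|---|---|
| 3 | 4.5% | 60.8% to 62.3% |
| 7 | 10.4% | 62.7% to 66.1% |
| 10 | 14.9% | 64.5% to 69.4% |
| 13 | 19.4% | 66.8% to 73.2% |

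**With the fix.** If stopping without inactive disease is a competing event, and no one is censored before R12 for another reason, the cumulative incidence at R12 is 40/67 = 59.7% in every row.

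**The case against.** The strongest reply is that the retreatment question already has an answer without this defect. The LOCF proportion carries a non-achieving value forward (SAP 5.3), so a subject who stops without recovering stays in the denominator as a non-responder. That stands, and it limits what is at stake. It does not repair the curve, and the observed-case version drops stoppers from later visits and can drift upward in a similar way.

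A reader might infer that the plan definitely overstates recovery. The documents do not support that. They give no dropout rate; the effect is zero without early stopping; and Kaplan-Meier is not biased if stopping is unrelated to later recovery. The 13-stopper case needs 13 of 27 non-achievers (48%) to leave within 12 weeks. Protocol 6.8 also keeps subjects who ask to stop treatment in follow-up, so stopping drug does not always end assessment.

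A reader might also infer that the median will be too short, or that the sized 60% recovery estimate is biased. The first happens only in the largest split scenario in the first table. The second confuses two endpoints.

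It can be said that Kaplan-Meier is only inferred. That is correct, but a censoring rule has meaning only for an estimator that uses censoring, and the silence is itself a gap to close.

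Finally, counting every stopper as not recovered answers a somewhat different question and may understate what retreatment could achieve. That is a fair cost, and it is why the present rule should remain as a sensitivity analysis.

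**Conclusion.** The point holds conditionally. The rule in SAP 3.2 censors early stoppers as if their later chance of recovery matched that of subjects still on retreatment. Two conditions are needed for an upward bias: a censoring-based estimator, and a lower chance of recovery among those who stop. Both are plausible, but the documents establish neither.

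On the plan's figures and the 20/12/8 timing, the excess is about 2 points with 4 stoppers and about 9 with 13. Across all the timings tried, it is about 3 to 6 points with 7 stoppers and about 7 to 14 with 13. The finding is confined to one secondary curve in a single-arm estimation study. The primary endpoint and the LOCF recovery proportion are untouched. The case for a change is that a better-defined estimator costs almost nothing.

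**What to change.** In SAP 3.2, with a matching entry in SAP section 6:

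- Name the estimator: a cumulative incidence function (Aalen-Johansen) for ASDAS inactive disease from the first retreatment dose, with discontinuation of retreatment without inactive disease as a competing event. Equivalently, keep such subjects at risk as non-achievers to the end of the R12 analysis window. Day 84 is too early a limit: the R12 visit may fall up to 4 days later (Schedule of Activities), and the SAP Appendix 2.3 window runs to the end of the period. Stoppers would leave the risk set before late R12 assessments, and part of the bias would return.
- Continue to censor subjects who complete R12 without inactive disease at R12. Loss to follow-up unrelated to treatment may also stay censored if the SAP says so in advance.
- Report cumulative incidence at R12 with its 95% interval, together with the number of early stoppers and their reasons. SAP 6.3.2 already tabulates discontinuations by period and reason.
- Keep the present censoring rule as a sensitivity analysis.

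The cost is a sentence or two of SAP text and no new data. Reported recovery may be a few points lower, and a subject who discontinues retreatment for an unrelated reason counts as not having recovered on it.
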